10.4.2.1 Safety Analyses

1058 All randomized participants will be included in these analyses and the circumstances of all
1059 reportable cases of the following will be summarized and tabulated by treatment group:

1060 • Severe hypoglycemia
1061 • Diabetic ketoacidosis
1062 • Other serious adverse events and serious adverse device events
1063 • Unanticipated adverse device effects

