293 parameters on the CLC AP system t:slim X2 with Control-IQ technology for use both at ski
294 camp and at home in adolescent patients with type 1 diabetes.

295 Primary Specific Aim:

296 To assess the safety and feasibility of using insulin parameters as determined by MyTDI during
297 normal outpatient conditions in the t:slim X2 with Control-IQ Technology AP system.

298 Secondary Specific Aims:

299 To assess the safety and feasibility of using insulin parameters as determined by MyTDI during
300 intense exercise outpatient conditions in the t:slim X2 with Control-IQ Technology AP system.

301 **1.3 Potential Risks and Benefits of the Investigational Device**

302 Risks and Benefits are detailed below. Loss of confidentiality is a potential risk; however, data
303 are handled to minimize this risk. Hypoglycemia, hyperglycemia and ketone formation are
304 always a risk in participants with type 1 diabetes and participants will be monitored for this.

305 **1.3.1 Known Potential Risks**306 **1.3.1.1 Venipuncture Risks**

307 A hollow needle/plastic tube will be placed in the arm for taking blood samples. Blood draws
308 can cause some common reactions like pain, bruising, or redness at the sampling site. Less
309 common reactions include bleeding from the sampling site, formation of a small blood clot or
310 swelling of the vein and surrounding tissues, and fainting.

311 **1.3.1.2 Fingerstick Risks**

312 About 1 drop of blood will be removed by fingerstick for measuring blood sugars and sometimes
313 HbA1c or other tests. This is a standard method used to obtain blood for routine hospital
314 laboratory tests. Pain is common at the time of lancing. In about 1 in 10 cases, a small amount
315 of bleeding under the skin will produce a bruise. A small scar may persist for several weeks.
316 The risk of local infection is less than 1 in 1000. This should not be a significant contributor to
317 risks in this study as fingersticks are part of the usual care for people with diabetes.

318 **1.3.1.3 Subcutaneous Catheter Risks (CGM)**

319 Participants using the CGM will be at low risk for developing a local skin infection at the site of
320 the sensor needle placement. If a catheter is left under the skin for more than 24 hours, it is
321 possible to get an infection where it goes into the skin, with swelling, redness and pain. There
322 may be bleeding where the catheter is put in and bleeding under the skin causes a bruise (1 in 10
323 risk).

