824 will not be asked to distinguish between device complaints and malfunctions.

825 **8.1.2 Reportable Adverse Events**

826 For this protocol, a reportable adverse event includes any untoward medical occurrence that
827 meets one of the following criteria:

828 1. A serious adverse event
829 2. An Adverse Device Effect as defined in section 8.1.1, unless excluded from reporting in
830 section 8.
831 3. An Adverse Event occurring in association with a study procedure
832 4. Hypoglycemia meeting the definition of severe hypoglycemia as defined below
833 5. Diabetic ketoacidosis (DKA) as defined below or in the absence of DKA, a hyperglycemic or
834 ketosis event meeting the criteria defined below

835 Hypoglycemia and hyperglycemia not meeting the criteria below will not be recorded as adverse
836 events unless associated with an Adverse Device Effect. Skin reactions from sensor placement
837 are only reportable if severe and/or required treatment.

838 Pregnancy occurring during the study will not be considered an adverse event.

839 **8.1.2.1 Hypoglycemic Events**

840 Hypoglycemia not associated with an Adverse Device Effect is only reportable as an adverse
841 event when the following definition for severe hypoglycemia is met: the event required
842 assistance of another person due to altered consciousness, and required another person to actively
843 administer carbohydrate, glucagon, or other resuscitative actions. This means that the participant
844 was impaired cognitively to the point that he/she was unable to treat himself/herself, was unable
845 to verbalize his/ her needs, was incoherent, disoriented, and/or combative, or experienced seizure
846 or coma. These episodes may be associated with sufficient neuroglycopenia to induce seizure or
847 coma. If plasma glucose measurements are not available during such an event, neurological
848 recovery attributable to the restoration of plasma glucose to normal is considered sufficient
849 evidence that the event was induced by a low plasma glucose concentration.

850 **8.1.2.2 Hyperglycemic Events/Diabetic Ketoacidosis**

851 Hyperglycemia not associated with an Adverse Device Effect is only reportable as an adverse
852 event when one of the following four criteria is met:

- 853 • the event involved DKA, as defined by the Diabetes Control and Complications Trial
854 (DCCT) and described below
- 855 • evaluation or treatment was obtained at a health care provider facility for an acute event

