856 involving hyperglycemia or ketosis
- 857 • blood ketone level ≥ 1.5 mmol/L and communication occurred with a health care provider at
858 the time of the event
- 859 • blood ketone level ≥ 3.0 mmol/L, even if there was no communication with a health care
860 provider

861 Hyperglycemic events are classified as DKA if the following are present:

862 • Symptoms such as polyuria, polydipsia, nausea, or vomiting;
863 • Serum ketones ≥ 1.5 mmol/L or large/moderate urine ketones;
864 • Either arterial blood pH < 7.30 or venous pH < 7.24 or serum bicarbonate < 15 ; and
865 • Treatment provided in a health care facility

866 All reportable Adverse Events—whether volunteered by the participant, discovered by study
867 personnel during questioning, or detected through physical examination, laboratory test, or other
868 means—will be reported on an adverse event form online. Each adverse event form is reviewed
869 by the Medical Monitor to verify the coding and the reporting that is required.

870 **8.1.3 Relationship of Adverse Event to Study Device**

871 The study investigator will assess the relationship of any adverse event to be related, possibly
872 related, or unrelated by determining if there is a reasonable possibility that the adverse event may
873 have been caused by the study device.

874 **8.1.4 Intensity of Adverse Event**

875 The intensity of an adverse event will be rated on a three point scale: (1) mild, (2) moderate, or
876 (3) severe. It is emphasized that the term severe is a measure of intensity: thus a severe adverse
877 event is not necessarily serious. For example, itching for several days may be rated as severe,
878 but may not be clinically serious.

879 • MILD: Usually transient, requires no special treatment, and does not interfere with the
880 participant's daily activities.

881 • MODERATE: Usually causes a low level of inconvenience or concern to the participant and
882 may interfere with daily activities, but is usually ameliorated by simple therapeutic measures.

883 • SEVERE: Interrupts a participant's usual daily activities and generally requires systemic
884 drug therapy or other treatment.

885 **8.1.5 Coding of Adverse Events**

886 Adverse events will be coded using the MedDRA dictionary. The Medical Monitor will review
887 the investigator's assessment of causality and may agree or disagree. Both the investigator's and
888 Medical Monitor's assessments will be recorded. The Medical Monitor will have the final say in

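### The by-arm safety table has no line for non-serious hyperglycemia/ketosis events without DKA or for non-serious procedure-related adverse events, although section 8.1.2 makes both reportable

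*Combined protocol and SAP*

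**What the plan says.** Section 10.4.2.1 includes all randomized participants and says that "reportable cases of the following will be summarized and tabulated by treatment group". The list that follows is closed: severe hypoglycemia, DKA, "Other serious adverse events and serious adverse device events" and "Unanticipated adverse device effects". There is no line for other reportable events.

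Section 8.1.2 sets five grounds for reporting an adverse event. Besides serious events and severe hypoglycemia, they include:

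- "An Adverse Device Effect as defined in section 8.1.1, unless excluded from reporting in" section 8;
- any adverse event linked to a study procedure;
- "Diabetic ketoacidosis (DKA) as defined below or in the absence of DKA, a hyperglycemic or" ketosis event meeting the stated criteria.

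Section 8.1.2.2 gives four criteria for hyperglycemia: DKA, evaluation or treatment at a health care facility, "blood ketone level ≥ 1.5 mmol/L and communication occurred with a health care provider at" the time of the event, and "blood ketone level ≥ 3.0 mmol/L, even if there was no communication with a health care" provider.

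The primary specific aim in section 1.2 is "To assess the safety and feasibility of using insulin parameters as determined by MyTDI during" normal outpatient conditions. Section 10.1 describes chapter 10 as the framework for a detailed analysis plan, to be finalized before data are first tabulated by treatment group.

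**The concern.** The randomized difference is a set of pump parameters: basal rate, correction factor and carbohydrate ratios (section 4.1.2). Section 1.3.1.5 says that hyperglycemia and ketonemia can follow when insulin delivery is attenuated or suspended for long. A ketosis event short of DKA is therefore a direct clinical sign of one way in which changed settings could do harm. The protocol takes the trouble to define and collect such events. If the safety analysis follows 10.4.2.1 as written, those that are not serious stay on the forms and out of the arm comparison, in a trial whose objective and primary aim both include safety.

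A related point is timing. Participants wear the study system for about 5 days before randomization, on their usual parameters, and adverse events are asked about in that period (sections 3.1, 3.1.2 and 3.1.5; Table 1). Section 10.4.2.1 does not say how those events enter a table laid out by treatment group.

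**Working it through.** No arithmetic in the plan bears on this point. The power figure in 10.3 concerns a baseline-to-home ANOVA comparison and does not depend on it. The check is to set what is reportable against what is tabulated.

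**Step 1. The five grounds in 8.1.2 against chapter 10.**

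| Reportable under 8.1.2 | Line in 10.4.2.1 | Other by-arm cover in chapter 10 |
|---|---|---|
| Serious adverse event | Yes | Not needed |
| Adverse device effect | Only if serious or unanticipated | Possibly 10.5, through 8.2 |
| Event linked to a study procedure | Only if serious | None of its own |
| Severe hypoglycemia | Yes | Not needed |
| DKA, or hyperglycemia/ketosis without DKA | DKA yes; otherwise only if serious | CGM percentages only; no ketone outcome |

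**Step 2. The four hyperglycemia criteria in 8.1.2.2.** One (DKA) has a line. The other 4 − 1 = 3 (facility care, ketones at or above 1.5 mmol/L with provider contact, ketones at or above 3.0 mmol/L) reach 10.4.2.1 only when the event is also serious.

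**Step 3. Whether another section fills the ketosis gap.** Section 10.4.2 lists CGM time below 50, 54, 60 and 70 mg/dL and above 180, 250 and 300 mg/dL, mean CGM, coefficient of variation, LBGI and HBGI, total insulin, hypoglycemic episodes, and the number and amount of rescue carbohydrate. None uses ketones. Section 10.5 covers device malfunctions and other reported device issues. Under 8.1.1 a complaint or malfunction happens to the device and an adverse event happens to the participant. Ketosis under the programmed settings, with the pump working to specification, is neither a complaint nor a malfunction. It could be classed as an adverse device effect if the device may have contributed, but even then 10.5 would not show it as ketosis.

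**Step 4. Whether non-serious adverse device effects are covered.** Section 8.2, headed as reportable device issues, includes adverse device effects among the things to be reported. Section 10.5 tabulates other reported device issues by treatment group. Read together, they may cover these effects. Read with the distinction in 8.1.1, they may not. The text does not settle it.

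**Step 5. Events before randomization.** The planned observation is about 5 days at home, 72 hours (3 days) at camp and about 5 days at home: 5 + 3 + 5 = 13 days. About 5/13 = 38% of it precedes randomization. Section 10.2 computes the outcomes for baseline, camp and final home segment, but 10.4.2.1 does not say that adverse events are divided in this way.

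**The case against.** The strongest objection is that the plan already compares over- and under-delivery of insulin between arms. This is largely right. The outcomes in 10.4.2 carry efficacy labels, but they measure low and high glucose exposure, hypoglycemic episodes, rescue carbohydrate and insulin use by arm and by period. They are likely to be more sensitive than event counts in about 10 participants per arm. A reader might infer from 10.4.2.1 alone that harm from wrong dosing goes uncompared; the documents do not support that. The new rows would also add little on hypoglycemia, because 8.1.2.1 makes non-severe hypoglycemia reportable only when it is tied to an adverse device effect. What remains is ketosis, which CGM does not measure.

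Four other tempting readings also go too far:

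- That non-serious adverse device effects are omitted. Sections 8.2 and 10.5 leave this unclear, so the plan needs clarification here.
- That whole classes of event are dropped. Any serious event still appears, and 8.1.1 lets the investigator judge an event significant enough to count as serious.
- That safety alone is the primary aim. Section 1.2 says safety and feasibility.
- That a table of rare events is uninformative because the arms are small. That is true of any empty row, including the ones proposed here, so it is no argument for these rows in particular.

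It can also be said that chapter 10 is only a framework, and that the medical monitor reviews each adverse event form and periodic compiled safety data (sections 8.1.2.2 and 8.5.2). Both are true, but neither commits anyone to the missing lines. No detailed analysis plan is among the documents.

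**Conclusion.** The point holds in a limited form. Non-serious hyperglycemia/ketosis events without DKA and non-serious procedure-related adverse events are reportable but have no by-arm line of their own in chapter 10, and no listed outcome uses ketones. In extent, this is three of the four hyperglycemia criteria in 8.1.2.2 and one further ground in 8.1.2, each for its non-serious part. The treatment of non-serious adverse device effects is unclear.

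How many events this touches cannot be derived, because the documents give no expected rates. Nor do they show that the omitted events would be more frequent than the listed ones. The conclusion rests on reading the list in 10.4.2.1 as complete and on the detailed analysis plan following it. It is a cheap improvement to the safety table and does not affect the primary analysis.

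**What to change.** In section 10.4.2.1, or in the detailed analysis plan before any tabulation by treatment group:

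- Tabulate by treatment group all adverse events reportable under 8.1.2, giving the number of events and the number of participants affected.
- Give separate lines to hyperglycemia/ketosis without DKA, as defined in 8.1.2.2, and to events linked to a study procedure.
- State whether the device-issue table in 10.5 counts non-serious adverse device effects; if it does not, add a line for them.
- List events that occurred before randomization separately, so that they are not attributed to an arm.

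The data are already on the adverse event forms, so the cost is a few more table rows. The counts will probably be sparse and should be presented as description, without formal comparison.

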10.5 Device Issues

1065 The following tabulations and analyses will be performed by treatment group to assess device
1066 issues:

1067 • Device malfunctions requiring study team contact and other reported device issues
1068 • Sensor performance metrics (difference, absolute relative difference, and International
1069 Organization for Standardization criteria) – if applicable, by sensor version.
1070 • % time CGM data available - overall and by month

1071 The following tabulations will be performed for the CLC arm only:

1072 • Performance metrics, describing the Control-IQ system and its components like:
1073 ♦ % time CGM data were available to the Control-IQ system – overall and by month

UNIVERSITY OF VIRGINIA

- 1074 ◆ % time in different operational modes per week - overall and by month
- 1075 ◆ Rate of different failure events and alarms per 24 hours recorded by the Control-IQ
- 1076 system – overall and by month
- 1077

1078 **Chapter 11: Data Collection and Monitoring**

1079 **11.1 Case Report Forms and Device Data**

1080 The main study data are collected through a combination of case report forms (CRFs) and
1081 electronic device data files obtained from the study software and individual hardware
1082 components. These electronic device files and electronic CRFs from the study website are
1083 considered the primary source documentation.

1084 When data are directly collected in electronic case report forms, this will be considered the
1085 source data. Each participating site will maintain appropriate medical and research records for
1086 this trial, in compliance with ICH E6 and regulatory and institutional requirements for the
1087 protection of confidentiality of participants.

1088 **11.2 Study Records Retention**

1089 Study documents should be retained for a minimum of 2 years after the last approval of a
1090 marketing application in an ICH region and until there are no pending or contemplated marketing
1091 applications in an ICH region or until at least 2 years have elapsed since the formal
1092 discontinuation of clinical development of the investigational product. These documents should
1093 be retained for a longer period, however, if required by local regulations. No records will be
1094 destroyed without the written consent of the sponsor, if applicable. It is the responsibility of the
1095 sponsor to inform the investigator when these documents no longer need to be retained.

1096 **11.3 Protocol Deviations**

1097 A protocol deviation is any noncompliance with the clinical trial protocol, GCP, or procedure
1098 requirements. The noncompliance may be either on the part of the participant, the investigator,
1099 or the study site staff. As a result of deviations, corrective actions are to be developed by the site
1100 and implemented promptly. The site PI/study staff is responsible for knowing and adhering to
1101 their IRB requirements.

1102 **Chapter 12: Ethics/Protection of Human Participants**

1103 **12.1 Ethical Standard**

1104 The investigator will ensure that this study is conducted in full conformity with Regulations for
1105 the Protection of Human Participants of Research codified in 45 CFR Part 46, 21 CFR Part 50,
1106 21 CFR Part 56, and/or the ICH E6.

1107 **12.2 Institutional Review Boards**

1108 The protocol, informed consent form(s), recruitment materials, and all participant materials will
1109 be submitted to the IRB for review and approval. Approval of both the protocol and the consent
1110 form must be obtained before any participant is enrolled. Any amendment to the protocol will
1111 require review and approval by the IRB before the changes are implemented to the study. All
1112 changes to the consent form will be IRB approved; a determination will be made regarding
1113 whether previously consented participants need to be re-consented.

1114 **12.3 Informed Consent Process**

1115 **12.3.1 Consent Procedures and Documentation**

1116 Informed consent is a process that is initiated prior to the individual's agreeing to participate in
1117 the study and continues throughout the individual's study participation. Extensive discussion of
1118 risks and possible benefits of participation will be provided to the participants and their families.
1119 Consent forms will be IRB-approved. The participant will be asked to read and review the
1120 document. The investigator will explain the research study to the participant and answer any
1121 questions that may arise. All participants will receive a verbal explanation in terms suited to
1122 their comprehension of the purposes, procedures, and potential risks of the study and of their
1123 rights as research participants. Participants will have the opportunity to carefully review the
1124 written consent form and ask questions prior to signing.

1125 The participants should have the opportunity to discuss the study with their surrogates or think
